## 10.6.2 Adverse Events

Analysis set: Safety

Note:

- If needed, adverse event data may be presented for all patients.
- The dose reduction information will be compiled using the treatment exposure page and AE page of eCRF through common AE number.

The frequency of adverse events (AEs) will be computed by counting each patient only once per MedDRA [Version 24.0] preferred term and according to the maximum NCI CTCAE v.5.0 grade attained by the patient over the specified period. The percentage of patients with an event will be calculated using the number of patients in the safety analysis set as the denominator.

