Study Treatment	
For purposes of this study, each cycle of therapy consists of 4 weeks.
 
Tenalisib: Tenalisib will be administered from Day 1-28 in 28-days of cycle up to C8D1 in absence of disease progression and unacceptable toxicity. However, in Cycle 1 of Dose Escalation, Tenalisib will be started from Day 3 to permit pharmacokinetic analysis of Romidepsin alone prior to combination treatment.

	
Tenalisib tablets will be self-administered orally twice daily one hour before a major meal (e.g. breakfast and dinner). Patients should not consume food during this one-hour period. On the day of Romidepsin therapy, the morning dose of Tenalisib will be given in clinic one hour prior to Romidepsin infusion.
 
Romidepsin: Romidepsin will be administered intravenously (IV) over a 4-hour period on days 1, 8 and 15 in a 28-day cycle.

Statistical Analysis	
Part 1: In Dose Escalation, three patients per cohort are considered appropriate for the assessment of overall safety and tolerability and for providing adequate confidence for dose escalation. No formal sample size and power analysis is done. Accordingly, total 2-18 patients will be enrolled in 3 escalating cohorts unless additional dose levels are required to reach MTD/ optimal dose. Optimal dose will be determined by the SRC.
 
Part 2: Total 24 patients with relapsed/refractory TCL will be enrolled in two groups (12 patients in each group).
 
The SRC may modify the sample size due to unforeseen clinical situations.

GENERAL INFORMATION	
SPONSOR	[REDACTED]
PRINCIPAL INVESTIGATOR AND STUDY CHAIR	[REDACTED]
CO- PRINCIPAL INVESTIGATOR	[REDACTED]
SPONSOR'S REPRESENTATIVE	[REDACTED]
SPONSOR'S MEDICAL EXPERT	[REDACTED]
STATISTICIAN	[REDACTED]
CLINICAL PK, BIOMARKER LABORATORY	[REDACTED]

List of Abbreviations

AE	Adverse Event
ALP	Alkaline Phosphatase
ALT (SGOT)	Alanine aminotransferase
ANC	Absolute Neutrophil Count
aPTT	Activated Partial Thromboplastin Time
Allo-SCT	Allogeneic Hematopoietic Stem Cell Transplantation
AST (SGPT)	Aspartate aminotransferase
AUC _{0-t}	Area Under the plasma-concentration time curve from zero up to the last measurable concentration
BID	Twice Daily
β-HCG	β-human chorionic gonadotropin
BSA	Body Surface Area
C _{max}	Peak Drug Concentration
CBC	Complete Blood Count
CMV	Cytomegalovirus
CNS	Central Nervous System
CR	Complete Response
CrCl	Creatinine Clearance
CT	Computed Tomography
CTCAE	Common Terminology Criteria for Adverse Events

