7.6.3 Determination of Dose-limiting toxicity

The patient population used for determination of MTD will consist of patients who have met the minimum safety evaluation requirements of the study, and/or who have experienced a DLT. The data of at least 3 patients will be required for DLT assessment.

- DLT assessment period will be 28-days (inclusive) (will begin on C1D1 and end on C2D1), unless extended by the medical monitor.
- Patients must have been treated with at least 2 doses of Romidepsin and minimum 14 days with Tenalisib in the first cycle to be considered eligible for safety assessment unless identified to have a DLT.
- *Patients experiencing DLT after initiating combination will be considered evaluable regardless of the number of doses received (Please note Romidepsin alone will be administered on Day 1, therefore patient will not be considered for MTD assessment if patient develops DLT on these days).*

If a patient withdraws from the study during Cycle 1 due to any reason other than DLT (e.g. disease progression or consent withdrawal) and does not meet the minimum requirements for inclusion in the MTD-determining population described above will be replaced.

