### Dose escalation scheme:

Cohort	N	Tenalisib 	Romidepsin 
Cohort 1	3-6	Tab. 400 mg PO twice a day	IV 12 mg/m  on Day 1, 8 and 15
Cohort 2	3-6	Tab. 600 mg PO twice a day	IV 12 mg/m  on Day 1, 8 and 15
Cohort 3	3-6	Tab. 800 mg PO twice a day	IV 14 mg/m  on Day 1, 8 and 15

Note: Alternate dose levels/dosing schedules may be considered by the SRC if deemed essential based on emerging safety and PK data.

In case the dose (e.g. 800 mg BID) is leading to DLT of the combination, the dose of Tenalisib will be reduced to lower dose (e.g. 600 mg BID) and will be evaluated for safety in a separate cohort.

In case the dose (e.g. 14 mg/m^2) is leading to DLT of the combination, the dose of Romidepsin will be reduced to lower dose (e.g. 12 mg/m^2) and if required further to 10 mg/m^2 and will be evaluated for safety in a separate cohort.

**DLT assessment:** The data of at least 3 patients will be required for DLT assessment. DLT assessment period will be 28-days (inclusive) (will begin on C1D1 and end on C2D1), unless extended by the medical monitor. In the first cycle, patients must have been treated with at least 2 doses of Romidepsin and minimum 14 days with Tenalisib to be considered eligible for safety analysis unless identified to have a DLT. Patients who experience a DLT will be considered evaluable regardless of the number of doses received.

Individual patients will be considered for **Intra-subject dose escalation** at the discretion of investigator after discussion with medical monitor.

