### 7.2 Safety Population Set

*The Safety Population set will include all subjects who receive at least 1 dose of the study medication.* This set will be used for reporting safety data, patient demographic data and any available patient baseline characteristics as reported in the Case Report Form (CRF).

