### **Standard Summaries of Adverse Events**

Treatment Emergent Adverse Events (TEAEs) are those that start on or after the date of first dose of study medication.

An overall summary of TEAEs (number and percentage of patients along with the number of events) will be presented with the following:

- Any TEAE
- Treatment Related TEAEs
- Serious TEAEs
- Treatment Related Serious TEAEs
- Grade 3 or 4 TEAEs
- Treatment Related Grade 3 or 4 TEAEs
- DLTs (Note: Applicable for dose escalation phase only)
- TEAEs leading to drug interruptions
- Related TEAEs leading to drug interruptions
- Serious TEAEs leading to drug interruptions
- Treatment Related Serious TEAEs leading to drug interruptions
- TEAEs leading to dose reduction
- Related TEAEs leading to dose reduction
- Serious TEAEs leading to dose reduction
- Treatment Related Serious TEAEs leading to dose reductions

- TEAEs leading to drug withdrawn permanently
- Treatment Related TEAEs leading to drug withdrawn permanently
- Serious TEAEs leading to drug withdrawn permanently
- Treatment Related Serious TEAEs leading to drug withdrawn permanently
- Fatal TEAEs
- Treatment Related Fatal TEAEs
- Protocol-Defined Adverse Events of Special Interest:
  - Pregnancy, abortion, birth defects/congenital anomalies
  - Overdose

Summaries showing the number of patients (n, %) along with number of events by SOC and PT will be provided for the following:

- DLTs (Note: Applicable for dose escalation phase only)
- TEAEs
- Related TEAEs
- Non-TEAEs
- Grade 3, 4 and 5 TEAEs
- Related Grade 3, 4 and 5 TEAEs
- Treatment-Emergent SAEs
- Related Treatment –Emergent SAEs
- TEAE with maximum CTCAE grade
- Treatment-Related TEAEs with maximum CTCAE grade per suspected drug(s) [Tenalisisib, Romidepsin or Combination]
- Deaths
- TEAEs leading to drug interruptions
- TEAEs leading to dose reduction
- TEAE leading to drug withdrawn permanently

The adverse events data will also be listed for individual patients.

- Any non-TEAE
- TEAEs
- Related TEAEs
- SAEs
- Treatment Emergent Grade 3, 4 and 5 AEs
- Treatment Related Grade 3, 4 and 5 AEs
- Treatment Related SAEs
- TEAEs leading to drug interruptions
- TEAEs leading to dose reduction
- TEAE leading to drug withdrawn permanently

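### Escalation DLT percentages are taken over the Safety set, not over the patients who determine the MTD

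*SAP*

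**What the plan says.** **Reporting.** SAP 10.6.2 works on the Safety set and states: "The percentage of patients with an event will be calculated using the number of patients in the safety analysis set as the denominator". SAP 7.2 defines that set: "The Safety Population set will include all subjects who receive at least 1 dose of the study medication". DLTs appear twice among the tables of number and percentage, once in the overall summary and once by SOC and PT, each time as "DLTs (Note: Applicable for dose escalation phase only"). Neither row is given a denominator of its own. Protocol 9.4.2 agrees with this: it lists DLT incidence first among the safety endpoints and bases the safety analyses on patients with at least one dose.

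**Dose finding.** Protocol 7.6.3 uses a different population: "The patient population used for determination of MTD will consist of patients who have met the minimum safety evaluation requirements of the study", and/or who had a DLT. The minimum is 2 Romidepsin doses and 14 days of Tenalisib in Cycle 1. The replacement rule begins "If a patient withdraws from the study during Cycle 1 due to any reason other than DLT" and applies when that minimum was not met. Protocol 7.6.4 then defines the MTD by 0 of 3 or 1 of 6 patients with a DLT.

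**Analysis sets.** Protocol 9.3 defines mITT, PP and Safety; SAP Section 7 adds All Enrolled. Neither has a DLT-evaluable set. SAP 5.1 repeats the minimum-exposure rule but attaches it to no set.

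**Lead-in.** The synopsis says: "However, in Cycle 1 of Dose Escalation, Tenalisib will be started from Day 3 to permit pharmacokinetic analysis of Romidepsin alone". Protocol 7.6.3 accordingly makes a DLT patient evaluable only if the DLT came after the combination began, and adds: "Romidepsin alone will be administered on Day 1, therefore patient will not be considered for MTD assessment if patient develops DLT on these days". The synopsis and SAP 5.1 carry no such limit: "Patients who experience a DLT will be considered evaluable regardless of the number of doses received". All three places open the DLT window on C1D1.

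**The concern.** Establishing the MTD is part of the primary objective, and the DLT table is where a reader of the study report will look for its basis. A patient who took one dose and left early for another reason says almost nothing about Cycle 1 tolerability, which is why 7.6.3 replaces such patients. The SAP table keeps them in the denominator with no DLT in the numerator. Whenever a cohort has at least one DLT and at least one replaced patient, the reported percentage is lower than the one that was set against the escalation rule.

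The evaluability sentence is a second, smaller mismatch. If it is read alone in the synopsis or SAP 5.1, a toxicity on the Romidepsin-alone days could be tabulated as a DLT of the combination, although 7.6.3 takes that patient out of MTD assessment.

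**Working it through.** **The plan's own figures.** Three cohorts of up to six give 3 × 6 = 18, the stated escalation maximum. The MTD rule corresponds to 0/3 = 0% or 1/6 = 16.7%. The MTD is exceeded at 2/6 = 33.3% or 2/3 = 66.7%. The documents state no DLT rate and no replacement rate.

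**Denominator.** Let d be DLTs in a cohort, e patients evaluable under 7.6.3, and r patients dosed but replaced.

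- Rate under 7.6.3: d / e
- Rate under SAP 10.6.2: d / (e + r)

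| 7.6.3 rate | SAP rate, r = 1 | r = 2 | r = 3 |
|---|---|---|---|
| 1/6 = 16.7% | 1/7 = 14.3% | 1/8 = 12.5% | 1/9 = 11.1% |
| 2/6 = 33.3% | 2/7 = 28.6% | 2/8 = 25.0% | 2/9 = 22.2% |
| 2/3 = 66.7% | 2/4 = 50.0% | 2/5 = 40.0% | 2/6 = 33.3% |

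With d = 0 or r = 0 the two rates are equal.

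**How often a replacement would occur.** Assume a proportion u of patients is not evaluable, independently between patients. A cohort that needs n evaluable patients has at least one replacement with probability 1 − (1 − u)^n.

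| Assumed u | n = 3 | n = 6 |
|---|---|---|
| 5% | 1 − 0.95³ = 14.3% | 1 − 0.95⁶ = 26.5% |
| 10% | 1 − 0.90³ = 27.1% | 1 − 0.90⁶ = 46.9% |
| 20% | 1 − 0.80³ = 48.8% | 1 − 0.80⁶ = 73.8% |

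So a replacement somewhere in escalation would not be unusual.

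**Lead-in.** Tenalisib starts on Day 3, so Days 1 and 2 are Romidepsin alone. Suppose one patient is recorded with a DLT on Day 1 and three others are evaluable and clean. Protocol 7.6.3 gives 0/3. The SAP table gives 1/4 = 25.0%, an error in the opposite direction. This requires the event to be recorded as a DLT at all, and three features of Protocol 7.6 make that uncommon:

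- Section 7.6 counts a toxicity as dose-limiting only if it is judged related to the combination.
- The hematologic criteria in 7.6.1 need non-resolution within 14 days, and the treatment-delay criterion in 7.6.2 needs at least 14 days. ALT/AST elevation is exempt if it resolves to Grade 2 or less within 14 days. None of these can be met by Day 2.
- Section 7.6.2 also exempts a single Grade ≥3 infusion reaction and Grade 3 nausea.

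**The case against.** The best defence of the SAP is that it follows the protocol: 9.4.2 lists DLT incidence among safety endpoints based on patients with at least one dose. The output is descriptive. The SRC decides on patient counts during the trial, so no percentage in the report can move a dose. The tables print counts beside percentages, disposition is shown by cohort with reasons for dropout, and SAP Section 14 lists exposure and discontinuations. One replacement at 1/6 costs only 16.7 − 14.3 = 2.4 points.

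Most of this stands. The mismatch lies inside the protocol as well as in the SAP, and it concerns reporting only. What does not stand is that the existing outputs are enough. The DLT count is visible, but the evaluable count to set it against is not. No output marks evaluability, the individual AE listings in 10.6.2 have no DLT line, and the analysis-population listing cannot show a set that was never defined. A reader would have to rebuild it by hand from exposure data.

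Two stronger readings are tempting. A reader might infer that the looser sentence in the synopsis and SAP 5.1 could change a dose decision. The documents do not support giving that much weight: the combination-relatedness requirement in 7.6, the SRC's discretion in 7.6.2 to count or discount an event, and the 14-day criteria largely contain it. The SAP is also dated 9 August 2021, against a protocol amendment of 30 November 2018 and about 10 months planned for escalation. The documents do not say that escalation was complete by then, but influence on it through SAP 5.1 is doubtful.

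A reader might also infer that a patient removed for a Day 1 DLT has no replacement rule, because the replacement sentence covers withdrawals for other reasons. But 7.6.3 requires data from at least 3 patients and 3.2.1.1 at least three per dose level, so that place has to be filled.

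**Conclusion.** The denominator point holds. Escalation DLT percentages will be computed on a wider population than the one that sets the MTD. They will be too low against the 0/3 or 1/6 rule in any cohort with both a DLT and a replaced patient. One replacement lowers the figure by 2.4 points at 1/6, from 33.3% to 28.6% at 2/6, and from 66.7% to 50.0% at 2/3. How often this happens depends on a replacement rate that the documents do not give. Dose assignment is not affected.

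The missing lead-in limit in the synopsis and SAP 5.1 is a real but minor inconsistency. It should be tidied at the same time. Both changes are worth making because they cost little and let the reported rate be traced to the dose decision.

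**What to change.** 1. **SAP Section 7:** add a DLT-evaluable set that mirrors Protocol 7.6.3. It holds escalation patients with at least 2 Romidepsin doses and 14 Tenalisib days in Cycle 1, or with a DLT after the combination started.
2. **SAP 10.6.2:** use this set as the denominator for the two DLT rows only. Add a footnote giving the number dosed, the number evaluable, and the number excluded with reasons. All other AE tables stay on the Safety set, so no event is lost from view.
3. **Synopsis and SAP 5.1:** replace the evaluability sentence with the 7.6.3 wording, copied verbatim, and state that the days it refers to are Days 1 and 2.
4. **Scope of the exclusion:** leave a patient out only when the DLT criteria are met during the Romidepsin-alone days. Onset before the first Tenalisib dose is not enough. Grade 4 thrombocytopenia that starts on Day 2 and becomes dose-limiting on the combination should stay evaluable, subject to SRC review. Excluding by onset would go beyond 7.6.3 and would be less cautious.

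The cost is one set definition, one denominator for two existing rows, one footnote and one aligned sentence in two places. Dose dates and AE dates are already needed for the planned outputs, and SAP Section 2 allows the SAP to modify the protocol's analysis plan. The dose levels, schedule and 3+3 rule do not change. The downside is that cohort DLT percentages rest on 3 to 6 patients and look slightly higher when someone was replaced.

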### **Standard Summaries of Adverse Events**

Treatment Emergent Adverse Events (TEAEs) are those that start on or after the date of first dose of study medication.

An overall summary of TEAEs (number and percentage of patients along with the number of events) will be presented with the following:

- Any TEAE
- Treatment Related TEAEs
- Serious TEAEs
- Treatment Related Serious TEAEs
- Grade 3 or 4 TEAEs
- Treatment Related Grade 3 or 4 TEAEs
- DLTs (Note: Applicable for dose escalation phase only)
- TEAEs leading to drug interruptions
- Related TEAEs leading to drug interruptions
- Serious TEAEs leading to drug interruptions
- Treatment Related Serious TEAEs leading to drug interruptions
- TEAEs leading to dose reduction
- Related TEAEs leading to dose reduction
- Serious TEAEs leading to dose reduction
- Treatment Related Serious TEAEs leading to dose reductions

- TEAEs leading to drug withdrawn permanently
- Treatment Related TEAEs leading to drug withdrawn permanently
- Serious TEAEs leading to drug withdrawn permanently
- Treatment Related Serious TEAEs leading to drug withdrawn permanently
- Fatal TEAEs
- Treatment Related Fatal TEAEs
- Protocol-Defined Adverse Events of Special Interest:
  - Pregnancy, abortion, birth defects/congenital anomalies
  - Overdose

Summaries showing the number of patients (n, %) along with number of events by SOC and PT will be provided for the following:

- DLTs (Note: Applicable for dose escalation phase only)
- TEAEs
- Related TEAEs
- Non-TEAEs
- Grade 3, 4 and 5 TEAEs
- Related Grade 3, 4 and 5 TEAEs
- Treatment-Emergent SAEs
- Related Treatment –Emergent SAEs
- TEAE with maximum CTCAE grade
- Treatment-Related TEAEs with maximum CTCAE grade per suspected drug(s) [Tenalisisib, Romidepsin or Combination]
- Deaths
- TEAEs leading to drug interruptions
- TEAEs leading to dose reduction
- TEAE leading to drug withdrawn permanently

The adverse events data will also be listed for individual patients.

- Any non-TEAE
- TEAEs
- Related TEAEs
- SAEs
- Treatment Emergent Grade 3, 4 and 5 AEs
- Treatment Related Grade 3, 4 and 5 AEs
- Treatment Related SAEs
- TEAEs leading to drug interruptions
- TEAEs leading to dose reduction
- TEAE leading to drug withdrawn permanently

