6.3 Screening

Written informed consent must be obtained ≤ 30 days prior to the initiation of trial treatment and before any protocol-specific procedures are performed. (The first day of trial treatment will be considered as C1D1.) Patients should be re-consented in the case that informed consent is obtained >30 days prior to the initiation of trial treatment. Screening vitals, laboratory tests, as described in the Schedule of Events, will be performed as per institutional practice and will be reviewed by the site PI/designee. The laboratory tests should be done ≤ 7 calendar days prior to the initiation of trial treatment. Re-screening can be done at the discretion of PI. Scans and other investigations to document measurable disease should be performed within 28 days prior to C1D1.

Lymphoma diagnosis should be made on the basis of morphology, immunohistochemistry, and flow cytometry reviewed by an experienced lymphoma pathologist. Appropriate, molecular studies should be considered to accurately categorize the lymphoma. For CTCL, the histopathologic diagnosis should be confirmed in a skin biopsy representative of current disease by a pathologist with expertise in cutaneous lymphoma. For Sezary patients, the diagnosis should be based on skin and blood criteria (defined as meeting T4 plus B₂ criteria) ([Appendix D](#)).

Clinical assessments of patients will include ECOG performance status ([Appendix A](#)), lymph nodes, organomegaly, and "B" symptoms. The staging of NHL/HL and CTCL patients will be done according to Ann Arbor ([Appendix G](#)) and ISCL/EORTC criteria ([Appendix E](#)) respectively [10]. CTCL patients will have half body global and up to 5 selected representative index lesions photographed at baseline.

Table 3: Summary of Key Assessments at Screening

Procedures	PTCL	CTCL
Lab investigation	√	√
ECG	√	√
Bone marrow biopsy	√ ¹	In case of patients with blood involvement (B ₂) ²
Radiological assessment ³	√	In case of nodal/visceral involvement
Skin assessment (mSWAT)	-	√
Skin biopsy	-	√
Skin photograph	-	√
Biomarker	√	√

1. A bone marrow biopsy and/or aspirate should be collected ≤ 3 months prior to C1D1.
2. A bone marrow biopsy will be done unless it has been shown to be negative within the last 6 months.
3. The scan and other investigations to document measurable disease should be performed within 28 days prior to C1D1.

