6.3.3 Prior and Concomitant Medication Review

Prior medication: The investigator/qualified designee will review prior medication use, including any protocol-specified washout requirement, and record prior medication taken by the subject within 28 days before starting the trial (i.e. C1D1). Treatment for the disease for which the subject has enrolled in the study will be recorded separately and not listed as a prior medication.

Concomitant medication: The investigator or qualified designee will record medication, if any, taken by the subject during the trial.

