6.3.5 Physical Examination

Full physical examination: The investigator/qualified designee will perform a complete physical exam during the screening period and as defined in Schedule of Events. Physical examination will include lymph node and systemic examination (General Appearance, HEENT, neck, cardiovascular, lungs, abdomen, lymph nodes, genitourinary, extremities, neurological, skin, and musculoskeletal). Physical examination also includes measurement of accessible nodal groups and the size of the spleen and liver. Clinically significant abnormal findings should be recorded as medical history.

Abbreviated (Directed) physical examination: For cycles that do not require a full physical exam per the Schedule of Events, the investigator or qualified designee will perform a directed physical exam as clinically indicated depending on assessment of tumor, prior to trial treatment administration. After the first dose of trial treatment new clinically significant abnormal findings should be recorded as AEs.

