7.1.2 Recording of Adverse Events

All adverse events of any patient during the course of the trial will be reported in the case report form, and the investigator will give his or her opinion as to the relationship of the adverse event to trial drug treatment (i.e., whether the event is related or unrelated to trial drug administration). If the adverse event is serious, it should be reported immediately to Sponsor. Other untoward events occurring in the framework of a clinical trial are also to be recorded as AEs (i.e., AEs that occur prior to assignment of trial treatment that are related to a protocol-mandated intervention, including invasive procedures such as biopsies, medication washout, or no treatment run-in).

All AEs regardless of seriousness or relationship to Tenalisib/Romidepsin, spanning from the informed consent drug until 30 calendar days after the last dose of study drug, discontinuation or completion of protocol-specific treatment as defined by the protocol for that patient, are to be recorded in the electronic Case Record Form (eCRF).

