7.4.2 Persistent or Recurrent Adverse Events

A persistent AE is one that extends continuously, without resolution, between patient evaluation time points. Such events should only be recorded once on the SAE Report Form and/or the AE eCRF, irrespective of severity. (E.g. If a persistent AE becomes more severe or lessens in severity, it should be recorded once with highest grade of severity on a SAE Report Form and/or AE eCRF).

A recurrent AE is one that occurs and resolves between patient evaluation time points, and subsequently recurs. All recurrent events should be recorded separately on an SAE Report Form and/or AE eCRF.

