7.4.3 Abnormal Laboratory Values

Any grade 3 or 4 laboratory abnormalities or any clinically significant grade 1 or 2 hematology or biochemistry laboratory value(s) should be recorded as an AE. Isolated laboratory abnormality without clinical significance should not be captured as AE if confirmed by the investigator. If an abnormal laboratory value or vital sign is associated with clinical signs and/or symptoms, the sign or symptom should be reported as an AE, and the associated laboratory value or vital sign should be considered additional information that must be collected on the relevant eCRF. If the laboratory abnormality is a sign of a disease or syndrome, only the diagnosis needs to be recorded on the SAE Report Form or AE eCRF.

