7.4.6 Pre-existing Medical Conditions

A pre-existing medical condition is one that is present at the start of the trial. Such conditions should be recorded on the General Medical History eCRF. A pre-existing medical condition should be recorded as an AE or SAE only if the frequency, severity, or character of the condition worsens during the trial. When recording such events on an SAE Report Form and/or AE eCRF, it is important to convey the concept that the pre-existing condition has changed by including applicable description.

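### TEAEs are defined by start date alone, so a pre-dose adverse event kept on one record is not counted as treatment-emergent when it worsens to Grade 3-4 on treatment

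*SAP*

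**What the plan says.** **Definition.** SAP 10.6.2, under the standard summaries: "Treatment Emergent Adverse Events (TEAEs) are those that start on or after the date of first dose of study medication". Neither document adds a clause for worsening.

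**Collection window.** Protocol 7.1.2 has adverse events recorded over a period "spanning from the informed consent drug until 30 calendar days after the last dose of study drug". Protocol 6.3 limits the gap between consent and dosing: "Patients should be re-consented in the case that informed consent is obtained >30 days prior to the initiation of trial treatment". Pre-dose adverse event records can therefore exist. The SAP expects them, since it plans a Non-TEAE table and listing.

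**Recording a persistent event.** Protocol 7.4.2 allows one record. If the severity changes, "it should be recorded once with highest grade of severity on a SAE Report Form and/or AE eCRF". It provides for no new record and no new start date at worsening.

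**A second recording route.** Under Protocol 7.4.6 a pre-existing condition is filed as medical history and becomes an adverse event "only if the frequency, severity, or character of the condition worsens during the trial". Protocol 6.3.5 also files screening findings as history and adds: "After the first dose of trial treatment new clinically significant abnormal findings should be recorded as AEs". Neither section says what onset date the later record carries.

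**What the rows report.** SAP 4.1 makes adverse events, Grade 3/4 events and serious and fatal events the primary endpoint.

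**The concern.** Treatment emergence is meant to capture what happens to patients once they are dosed, including deterioration of something already present. A start-date test captures new events only. Combined with the one-record rule, it places an on-treatment rise to Grade 3-4 outside these rows: any TEAE, related, serious, Grade 3-4, interruption, dose reduction, permanent withdrawal and maximum grade.

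Compared with a starts-or-worsens rule, the error runs one way: TEAE counts can only fall. Two sites seeing the same clinical course can also produce different counts, depending on how each records it. Outputs may then disagree without explanation. A dose reduction could appear in the disposition table (SAP 10.1, which has no TEAE condition) but not under TEAEs leading to dose reduction.

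The situation is plausible here. Protocol 4.1 admits patients with ALT/AST up to 3 x ULN, a range that Table 8 labels Grade 1. In the earlier T-cell lymphoma study (Protocol 1.1.2), AST/ALT elevation was the most frequent treatment-related event of Grade 3 or higher (n=12).

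The stakes are limited to descriptive safety reporting. SAP 9.1 tests no hypothesis, and no DLT, MTD or SRC rule uses a TEAE rate.

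**Working it through.** The plan states no figure on this point, so there is none to reproduce. The check has two parts.

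**1. Apply the SAP rule (TEAE if start date is on or after first dose) to the record types that Protocol 7.4.2 and 7.4.6 can produce.**

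| Record | Start date held | SAP class | In Grade 3-4 TEAE row? |
|---|---|---|---|
| A. Begins before dosing, persists, one record, reaches Grade 3 on treatment | Before first dose | Non-TEAE | No |
| B. Filed as history, adverse event opened and dated at worsening to Grade 3 | After first dose | TEAE | Yes |
| C. New Grade 3 event on treatment | After first dose | TEAE | Yes |
| D. Pre-dose event resolves, then recurs at Grade 3 (separate record under 7.4.2) | After first dose | TEAE | Yes |

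Only A is lost. A and B may describe the same clinical course and differ only in how the site recorded it.

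Other SAP rules do not rescue A:
- Start-date imputation (9.3.1) acts only on missing or partial dates.
- The maximum-grade counting rule (10.6.2) decides how an event is graded in a table, not whether its record is a TEAE.
- Both maximum-grade tables named in 10.6.2 are restricted to TEAEs, whereas Protocol 9.4.2 plans worst grades per patient for selected events with no start-date test.
- Laboratory summaries (10.6.3) give absolute values, with no grade or shift table.

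**2. Size of the loss per affected patient.** SAP 10.6.2 uses the number of patients in the safety set as the denominator. If k patients of type A have no other Grade 3-4 TEAE, the overall Grade 3-4 row falls by 100 x k/N points. Planned sizes come from the SAP 5.1 and 5.2 tables, and columns from SAP 10; 42 = 18 + 24 is the planned maximum. The values of k are assumptions.

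| Column | N | k = 0 | k = 1 | k = 2 |
|---|---|---|---|---|
| Escalation cohort, smallest | 3 | 0 | 1/3 = 33.3 | 66.7 |
| Escalation cohort, largest | 6 | 0 | 1/6 = 16.7 | 33.3 |
| Expansion group | 12 | 0 | 1/12 = 8.3 | 16.7 |
| All escalation, maximum | 18 | 0 | 1/18 = 5.6 | 11.1 |
| Both expansion groups | 24 | 0 | 1/24 = 4.2 | 8.3 |
| Overall, maximum | 42 | 0 | 1/42 = 2.4 | 4.8 |

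A Grade 3-5 preferred-term row loses 1/N when the patient has no other TEAE of Grade 3 or higher for that term.

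**The case against.** The strongest reply is that record type A may be rare or absent, because much of the protocol points to the history route.
- Protocol 6.3.3 equates the start of the trial with C1D1. Read with 7.4.6, a condition present at C1D1 is history, and its worsening is a later adverse event.
- Footnote 3 to both schedules of events takes history at screening and captures significant history at later visits as an adverse event.
- The first paragraph of 7.1.2 describes pre-treatment events as those tied to protocol-mandated procedures, and the 7.1.1 definition refers to subjects given a product.
- Inclusion criterion 8 requires prior-therapy toxicity, other than alopecia, to be Grade 1 or less.
- Protocol 7.4.3 narrows the pool of low-grade laboratory records: "any clinically significant grade 1 or 2 hematology or biochemistry laboratory value(s) should be recorded as an AE".

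These passages do limit how often the problem can arise. They do not remove it: none sets an onset date, the second paragraph of 7.1.2 covers all events from consent, and the history route is never reconciled with 7.4.2.

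A second reply is that the events remain visible. SAP 10.6.2 plans listings of SAEs, treatment-related SAEs and treatment-related Grade 3-5 events without a treatment-emergent label. Where applicable, the event also stays in the DLT and Deaths tables. This is correct, and at these sample sizes listings are readable. But listings are not incidence rates, and the Non-TEAE table states no grade split. A single record at highest grade also need not show that the grade was reached on treatment.

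A third reply is that 1/N is the cost of any one misclassified patient. That is fair: the figures give a scale per patient, not an expected bias.

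Finally, no document requires a starts-or-worsens rule, and SAP section 2 lets the SAP modify the protocol's plans. The point is therefore an avoidable undercount, not a contradiction.

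**Conclusion.** The concern holds. Followed as written, the start-date definition and the one-record rule together leave an on-treatment worsening to Grade 3-4 out of the TEAE-only rows that report the primary endpoint.

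The conclusion rests on two conditions: the event is held as an adverse event record that began between consent and first dose, and the site keeps it on that record with its original start date. If sites instead date the event at worsening, the effect is zero. The number of affected patients is unknown and may be zero, so no overall bias can be stated.

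The point should be corrected because the undercount runs in one direction and the remedy is cheap. It does not threaten dose decisions or any inferential result.

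**What to change.** 1. In SAP 10.6.2, replace the definition with: *A TEAE is an AE that starts, or worsens in CTCAE grade, on or after the first dose of either study drug.*
2. Before database lock, list every adverse event that started before first dose, was ongoing at first dose and has a recorded grade of 2 or higher (a recorded Grade 1 cannot have worsened). Ask the site for the grade at first dose and the date of worsening, and hold both as added fields on the same record, which respects Protocol 7.4.2. Classify by the answer. Footnote unresolved cases and give a sensitivity count that treats unresolved events of Grade 3 or higher as treatment-emergent.
3. Optional: have sites open a new record at worsening. This first needs a protocol amendment reconciling 7.4.2 and 7.4.6, with IRB/IEC submission (Protocol 11.1).

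Step 1 cannot work without step 2, because the single record holds only the highest grade. The wording turns on grade: a pre-dose event that becomes serious or leads to interruption with no change in grade would still be a non-TEAE.

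Steps 1 and 2 cost a revised SAP version before lock, two added fields and a few site queries. The reported Grade 3-4 rate may come out slightly higher.
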